### **8.1.3 Patient Reported Outcomes**

The handling of missing data for patient reported outcomes (PROs) will be as follows. The missing items of the FSS questionnaire will be imputed with the average score of the answered items as long as more than 50% of the items on the FSS are answered. For EQ-5D-3L index and VAS scores, no imputation will be performed for missing items.

The mean change from baseline will be summarized descriptively for the FSS total score and the EQ-5D-3L health index score and VAS score for each treatment arm. For each of these scores, mean change from Baseline to the final scheduled DB Treatment Period Visit (Week 8 or Week 16) will be compared between treatment arms using an analysis of

covariance (ANCOVA) model with treatment arm as a factor and baseline score as a covariate.

The cumulative number and percentage of subjects who have ever experienced an increase from baseline in the FSS total score of greater than or equal to 0.7 through each applicable timepoint will also be calculated for each treatment arm.

The analyses described above will also be performed separately for each geographic region. Additional analyses of PROs will be performed as useful and appropriate.

#### **8.1.4 HCV and HIV Resistance Analyses**

For subjects who, experience HCV virologic failure (on treatment virologic failure or post-treatment relapse), full length NS3/4A and NS5A genes from their available baseline samples will be sequenced by population or deep sequencing. For each DAA target, resistance associated signature amino acid variants will be identified by AbbVie Clinical Virology. An appropriate prototypic reference sequence will be used for comparison with sequences from samples.

Only samples with an HCV RNA level of  $\geq 1000$  IU/mL will undergo sequence analysis in order to allow accurate assessment of products of amplification. Therefore, if the HCV RNA level at the time of virologic failure or treatment discontinuation is  $< 1000$  IU/mL, the sample closest in time after failure/discontinuation with an HCV RNA level  $\geq 1000$  IU/mL will be used. Included time points for analyses on available samples from subjects who do not achieve SVR12 are 1) the sample closest in time after failure/discontinuation with an HCV RNA level of  $\geq 1000$  IU/mL, and 2) 24 weeks post-DAA treatment, provided that resistance-associated substitutions were detected by either population or deep sequencing at the time of failure/discontinuation.

The following definitions will be used in the HCV resistance analyses:

- Baseline variant: a variant (by population or deep sequencing) in a baseline sample determined by comparison of the amino acid sequence of the baseline

sample to the appropriate prototypic reference amino acid sequence for a given DAA target.

- Post-baseline variant by population or deep sequencing: an amino acid variant detected by population or deep sequencing in a post-baseline time point sample that was not detected by population or deep sequencing at baseline in the subject.
- Emerged variant by population or deep sequencing: a post-baseline variant that is observed in 2 or more subjects of the same HCV subgenotype by population or deep sequencing.

The following analyses will be performed for all subjects in Arm A who experience virologic failure and for subjects in Arm B who experience virologic failure during or after the OL Treatment Period:

The HCV amino acid sequence as determined by population or deep sequencing of available baseline samples will be compared to the appropriate prototypic reference amino acid sequence. A listing by subject of all baseline variants relative to prototypic reference sequence at signature resistance associated amino acid positions will be provided for each DAA target (NS3 and NS5A).

The following analyses will be performed for subjects who experience virologic failure and have post-baseline resistance data available:

The HCV amino acid sequence as determined by population or deep sequencing on the sample closest in time after virologic failure with an HCV RNA level of  $\geq 1000$  IU/mL will be compared to the baseline and appropriate prototypic reference amino acid sequence. Listings by subject of all post-baseline amino acid variants detected by population or deep sequencing relative to the baseline amino acid sequences will be provided for each DAA target (NS3 and NS5A). Listings by subject of all emerged variants by population or deep sequencing, by amino acid position and variants within a DAA target in a post baseline sample relative to the baseline amino acid sequence will be provided for each DAA target. In addition,

listings by subject of all post-baseline amino acid variants (by population or deep sequencing) at signature resistance-associated positions relative to the appropriate prototypic reference amino acid sequence will be provided for each DAA target (NS3 and NS5A).

The persistence of post-baseline variants at signature resistance-associated amino acid positions for each target (NS3 and NS5A) will be assessed by population or deep sequencing at Post-Treatment Week 24. Listings by subject and time point of all post-baseline variants relative to the baseline amino acid sequence will be provided for each DAA target (NS3 and NS5A).

If resistance-associated substitutions are not detected a given target for a subject at the time of failure, then that target may not be sequenced in subsequent samples from that subject.

HIV-1 drug resistance genotyping for protease, reverse transcriptase and integrase sequences may be performed for protocol-defined eligible specimens.

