#### **8.1.2.2 Secondary Efficacy Endpoints**

The secondary efficacy endpoints are:

- the percentage of Arm A subjects with on-treatment HCV virologic failure (defined as confirmed increase of > 1 log10 IU/mL above nadir during treatment, confirmed HCV RNA ≥ 100 IU/mL after HCV RNA < LLOQ)

during treatment, or HCV RNA  $\geq$  LLOQ at the end of treatment with at least 6 weeks of treatment), and

- the percentage of Arm A subjects with post-treatment relapse (defined as confirmed HCV RNA  $\geq$  LLOQ between end of treatment and 12 weeks after the last dose of study drug among subjects who completed treatment as planned with HCV RNA  $<$  LLOQ at the end of treatment, excluding re-infection), and
- the percentage of Arm A HCV/HIV co-infected subjects (determined at Screening) achieving SVR12.

For the analysis of relapse, a subject enrolled to receive 8 weeks of treatment is considered to have completed treatment if study drug duration is 52 days or more, and a subject enrolled to receive 16 weeks of treatment is considered to have completed treatment if study drug duration is 105 days or more.

The percentages of subjects with on-treatment HCV virologic failure, post-treatment relapse, and SVR12 will be calculated along with two-sided 95% Wilson score confidence intervals.

In addition, a summary of reason for SVR12 non-response (e.g., on-treatment virologic failure, relapse, re-infection) will be provided for the set of all Arm A subjects and for the set of HCV/HIV co-infected Arm A subjects.

The secondary endpoints will be summarized for the set of all Arm A subjects in the ITT population and for the Arm A subjects in each of the GT1-infected and GT2-infected groups.

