### 8.1.2.5 Additional Efficacy Endpoints

The following additional efficacy endpoints will be summarized for the set of all Arm A subjects in the ITT and mITT population(s) and for each of the GT1-infected and GT2-infected groups:

- The percentage of subjects with HCV RNA < LLOQ at each post-baseline visit in the DB Treatment Period (using data as observed);
- The percentage of subjects with SVR4;
- A summary of reason for SVR4 non-response (e.g., on-treatment virologic failure, relapse, re-infection);
- The percentage of subjects with SVR24;
- A summary of reason for SVR24 non-response (e.g., on-treatment virologic failure, relapse, re-infection);
- The percentage of subjects who relapsed after achieving SVR12.

The following additional endpoints will be summarized for the set of all subjects in the OL Population and for each of the GT1-infected and GT2-infected groups of the OL Population:

- The percentage of subjects with SVR12;
- A summary of reason for SVR12 non-response (e.g., on-treatment virologic failure, relapse, other);
- The percentage of subjects with SVR12 by HCV genotype and available subtype;
- The percentage of subjects with SVR12 by HIV co-infection status;
- The percentage of subjects with SVR12 by prior HCV treatment history (treatment-naïve and treatment-experienced, with further breakdown by type of prior HCV treatment experience);
- The percentage of subjects with SVR24;
- A summary of reason for SVR24 non-response (e.g., on-treatment virologic failure, relapse, re-infection);

- The percentage of subjects who relapsed after achieving SVR12;
- The percentage of subjects with HCV RNA < LLOQ at each post-baseline visit in the OL Treatment Period (using data as observed);
- The percentage of subjects with SVR4;
- A summary of reason for SVR4 non-response (e.g., on-treatment virologic failure, relapse, re-infection).

In the above analyses for SVR and relapse, the percentage of subjects with each endpoint among those receiving active treatment during the DB or the OL Treatment Period, as applicable, will be calculated along with a two-sided 95% Wilson score CI. The summaries listed above will also be presented by geographic region.

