10.8 HCV and HIV Resistance Analyses

For subjects who enroll in South Korea or Singapore, full length NS3/4A and NS5A from baseline samples will be sequenced by next generation sequencing (NGS). For subjects who enroll in South Korea or Singapore who experience HCV virologic failure (on-treatment HCV virologic failure or post-treatment relapse as defined in Section 10.1), full length NS3/4A and NS5A genes from the first sample after virologic failure with HCV RNA \geq 1000 IU/mL will be sequenced by NGS. For resistance analysis only, the last

sample collected before OL Day 1 will be considered the baseline sample for Arm B subjects. For genotype 1-infected subjects experiencing virologic failure who enroll in China, amino acids 1 – 181 in NS3 and 1 – 215 in NS5A from the baseline sample and the first sample after virologic failure with HCV RNA ≥ 1000 IU/mL will be sequenced by population sequencing. An appropriate subtype-specific prototypic reference sequence will be used for comparison with sequences from samples. Subjects who experience HCV virologic failure will be referred to as subjects in the primary virologic failure (PVF) population, and a listing by subject that includes HCV subtype, IL28B genotype, reason for SVR₁₂ non-response, time point(s) sequenced as closest to time of HCV virologic failure, and HCV RNA value at the HCV virologic failure time point(s) will be produced for these subjects. In addition, all listings described below will display HCV subtype, and reason for SVR₁₂ non-response in the subject identifier for each subject. A separate listing will delineate all subjects in the PVF population for whom no sequencing was performed (e.g., lost to follow-up while HCV RNA ≤ 1000 IU/mL).

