Analysis 3: In subjects who enroll in South Korea or Singapore, the SVR₁₂ rate will be calculated and compared using Fisher's exact test between subjects with or without polymorphisms at 15% detection threshold in NS3 only, in NS5A only, any in NS3, any in NS5A, any in NS3 or NS5A, any in NS3 and NS5A at the *key subset of amino acid positions*. Analysis will be performed by HCV genotype, subtype, and overall on the mITT-GT-VF population.

Analysis 4: The following analyses will be performed for subjects who enroll in South Korea or Singapore who do not achieve SVR₁₂ (with separate summaries for subjects in PVF and non-PVF populations) and have post-baseline resistance data available:

- Listings by subject of all *treatment-emergent substitutions* relative to the baseline amino acid sequences will be provided for each DAA target (NS3 and NS5A).
- Listings by subject of all *substitutions at signature amino acid positions* in a post-baseline time point for each DAA target (NS3 and NS5A).

Analysis 5: For subjects who enroll in China who experience virologic failure and have sequence data available, the following analyses will be conducted:

- A listing of all baseline polymorphisms at signature amino acid positions for each DAA target (NS3 and NS5A).
- Listings by subject of all post-baseline substitutions relative to the baseline amino acid sequence will be provided for each DAA target (NS3 and NS5A).
- Listings by subject of all emerged substitutions, by amino acid position and substitution within a DAA target in a post-baseline sample relative to the baseline amino acid sequence will be provided for each DAA target (NS3 and NS5A).
- Listings by subject of all post-baseline substitutions at signature amino acid positions relative to the appropriate prototypic reference amino acid sequence will be provided for each DAA target (NS3 and NS5A).

If resistance-associated substitutions are not detected in a given target for a subject at the time of failure/discontinuation, then that target may not be sequenced in subsequent samples from that subject.

HCV Genotype/Subtype

Phylogenetic analysis will be conducted on HCV sequence from all available baseline samples from subjects who enroll in South Korea or Singapore and genotype 1-infected

subjects experiencing virologic failure who enroll in China in order to accurately determine subtype.

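### SAP Analysis 4 leaves out South Korea and Singapore subjects who relapse after SVR12, although SAP 10.8 sequences them as virologic failures

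*Protocol*

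**What the plan says.** **SAP 10.1** defines Relapse24 as confirmed HCV RNA at or above LLOQ in the SVR24 window in a subject who achieved SVR12. It then says that post-treatment relapse comprises Relapse12, Relapse24 and Relapse overall.

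**SAP 10.8, opening paragraph**, has the first post-failure sample with HCV RNA of at least 1000 IU/mL sequenced by NGS for South Korea and Singapore subjects with "on-treatment HCV virologic failure or post-treatment relapse as defined in Section 10.1". Subjects with virologic failure form the PVF population. A by-subject PVF listing is planned, which shows the reason for SVR12 non-response and the time points sequenced.

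**SAP 10.8, Analysis 4**, opens "The following analyses will be performed for subjects who enroll in South Korea or Singapore who do not achieve" SVR12. It lists treatment-emergent substitutions and substitutions at signature positions after baseline, with PVF and non-PVF subjects shown separately.

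**SAP 10.8, Analysis 5**, covers China. It takes subjects with virologic failure and sequence data, with no SVR12 condition.

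**SAP 10.8, time-point sentence**, names the samples to be analysed only for subjects without SVR12.

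**Protocol 8.1.4** covers subjects who "experience HCV virologic failure (on treatment virologic failure or post-treatment relapse"), and introduces the post-baseline listings with "The following analyses will be performed for subjects who experience virologic failure and have post-baseline resistance data available". Its own time-point sentence begins "Included time points for analyses on available samples from subjects who do not achieve" SVR12.

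**The concern.** A subject who clears the virus through the SVR12 window and then relapses is a virologic failure under SAP 10.1 and is sequenced under SAP 10.8. That subject nevertheless cannot enter Analysis 4, because entry requires that SVR12 was not achieved. The sequence would be produced and then left out of the only regional tabulation designed to show it.

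Relapse after SVR12 is a named additional efficacy endpoint in both documents. Following the emergence and persistence of resistance for 24 weeks is a stated purpose of the Post-Treatment Period. In a trial expecting very few failures, each failure's post-baseline sequence carries a large part of the resistance evidence.

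**Working it through.** No figure in the plan is in dispute, so the main check is a trace of one case through the SAP. Take a subject in South Korea or Singapore who achieves SVR12, then has confirmed HCV RNA at or above LLOQ in the SVR24 window, with a sample of at least 1000 IU/mL and no reinfection.

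| Step | SAP rule | Result |
|---|---|---|
| Relapse24? | 10.1: relapse in the SVR24 window after SVR12 | Yes |
| Post-treatment relapse? | 10.1: Relapse12, Relapse24, Relapse overall | Yes |
| Post-failure sample sequenced? | 10.8: regional virologic failure, first sample of at least 1000 IU/mL | Yes |
| PVF population and PVF subject listing? | 10.8: all virologic failures | Yes |
| Analysis 1 (baseline polymorphisms)? | Regional ITT subjects | Yes |
| Analyses 2 and 3? | Baseline polymorphisms against SVR12 | No post-baseline content |
| Analysis 4 (post-baseline substitutions)? | Regional subjects without SVR12 | **No** |
| Analysis 5? | China only | No |

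The subject is sequenced but appears in no post-baseline substitution listing. The same subject enrolled in China with GT1 infection would meet the entry condition of Analysis 5.

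Two features of the SAP suggest a drafting slip. Where it means failure up to Post-Treatment Week 12 only, it says so (the additional endpoint in section 10.7); section 10.8 does not use that term. It also gives no reason for handling the two regions differently.

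**Size.** Planned regional enrolment (SAP Table 1) is 105 GT1 + 39 GT2 = 144 of 504 subjects (28.6%), with 96 in Arm A (70 GT1, 26 GT2) and 48 in Arm B. No GT3–6 subjects are planned there. The documents give no rate of relapse after SVR12, so an expected number of affected subjects cannot be computed. For scale, protocol Table 5 gives relapse to Week 12 after 8 weeks of treatment in non-cirrhotic subjects as 0/384 for GT1 and 2/195 for GT2:

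- Regional Arm A: 70 × 0/384 + 26 × 2/195 = 0.27.
- Regional Arms A and B, if every Arm B subject receives open-label drug: 105 × 0/384 + 39 × 2/195 = 0.40.

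With less than one early relapse expected, a single late relapser could be the region's only relapse with post-baseline sequence data.

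**The case against.** The strongest reply is that the authors meant resistance analysis to cover SVR12 non-responders throughout. The PVF listing, and the subject identifier in every later listing, carry the reason for SVR12 non-response. The non-PVF group is defined among subjects without SVR12. Analysis 4 splits SVR12 non-responders into PVF and non-PVF, and the time-point sentence has the same limit. The time-point sentence and the identifier apply to China too, which weakens the contrast with Analysis 5. This stands as evidence of what the authors may have assumed. It does not remove the inconsistency, because section 10.8 refers back to section 10.1, which names Relapse24 explicitly. If exclusion was intended, the sequencing trigger and the PVF definition should have been limited to Relapse12.

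Three stronger readings are tempting, and the documents do not support them.

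- **That the SAP departs from the protocol without saying so.** The protocol is ambiguous. Its secondary-endpoint definition counts HCV RNA at or above "LLOQ between end of treatment and 12 weeks after the last dose of study drug among subjects who completed treatment as planned", and its time-point sentence is limited to subjects without SVR12. Against that, its listing sentence has no SVR12 condition, and an additional endpoint is "The percentage of subjects who relapsed after achieving" SVR12, which treats late recurrence as relapse. With the protocol unclear, the absence of an entry in SAP 12.1 proves nothing.
- **That the subject vanishes from the resistance report.** The subject remains in the PVF listing, the baseline polymorphism listing and the Relapse overall summary of SAP 10.7. Only the post-baseline substitution listings are missing.
- **That the issue scales with all Arm A relapses.** Analysis 4 is regional. GT3–6 subjects are planned only in China, and SAP 10.8 provides for sequencing China failures only if they are GT1. Relapses expected in China GT3 or GT2 subjects are therefore no guide to the regional resistance data.

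**Conclusion.** The point holds as an inconsistency inside the SAP, between the relapse definition in 10.1 with the sequencing rule in 10.8 on one side and the entry condition of Analysis 4 on the other. It rests on reading the cross-reference to section 10.1 literally, and it applies only where a post-failure sample reaches 1000 IU/mL. The consequence is small. By-subject descriptive listings are affected, no primary or secondary endpoint changes, and the number of subjects concerned may be zero. It is worth correcting because the rule would omit exactly the sequence the plan calls for, in a region where any one relapse may be the only one.

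**What to change.** Make three edits to SAP 10.8; the protocol need not change.

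1. Define the Analysis 4 population as all regional PVF subjects (on-treatment failure, Relapse12, Relapse24 or Relapse overall) plus regional non-PVF subjects without SVR12, each with post-baseline resistance data.
2. Extend the time-point sentence to PVF subjects who relapse after SVR12, using the first sample after failure with HCV RNA of at least 1000 IU/mL.
3. For these subjects, show the relapse type in the listings in place of the reason for SVR12 non-response.

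The cost is a few lines of SAP text and a small change to the listing programs. No laboratory work is added, because the opening paragraph of section 10.8 already calls for sequencing of these samples.

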### **8.1.5 Safety**

All subjects who receive at least one dose of study drug will be included in the safety analyses. Safety data will be summarized for the set of all subjects and for each of the GT1-infected and GT2-infected groups; these summaries will also be performed separately for each geographic region. Safety data will also be summarized for the set of HCV/HIV co-infected subjects. For safety analyses, data from the active (Arm A) and placebo (Arm B) treatment arms during the DB Treatment Period will be summarized, and comparisons between Arms A and B will be performed, as appropriate. The data from the OL Treatment Period and PT Period will also be summarized, but no comparisons will be performed.

### **8.1.5.1 Adverse Events**

Adverse events (AEs) will be coded using the Medical Dictionary for Regulatory Activities (MedDRA). AE data will be summarized and presented using primary MedDRA system organ classes (SOCs) and preferred terms according to the version of the MedDRA coding dictionary used for the study at the time of database lock.

AEs will be presented for the following treatment groups: (1) double-blind active (Arm A in the DB Treatment Period), (2) double-blind placebo (Arm B in the DB Treatment Period), and (3) open-label active (OL Population Arm B). Treatment group comparisons refer to comparisons of events between double-blind active and double-blind placebo during the DB Treatment Period of the study. For the active treatment arm during the DB Treatment Period (Arm A), treatment emergent AEs are defined as any event that begins or worsens in severity after initiation of active study drug through 30 days after the last dose of active study drug. For the placebo arm (Arm B), treatment-emergent AEs during the DB Treatment Period are defined as any event that begins or worsens in severity after initiation of placebo through 30 days after the last dose of placebo and prior to OL Day 1 (if applicable). For subjects in the OL Population, treatment-emergent AEs are defined as any event that begins or worsens in severity after initiation of open-label study drug through 30 days after the last dose of open-label study drug.

The number and percentage of subjects in each treatment group with treatment-emergent AEs will be tabulated by primary MedDRA SOC and preferred term; comparisons between arms will be made using Fisher's exact test. The tabulation of the number of subjects with treatment-emergent AEs by severity grade and relationship to study drug DAAs also will be provided. Subjects reporting more than one AE for a given MedDRA preferred term will be counted only once for that term using the event with the most severe grade for the severity grade tables and the most related event for the relationship to study drug tables. Subjects reporting more than one type of event within a SOC will be counted only once for that SOC.

